15.6 Data collected during follow-up period

Once a year the following data will be collected:

- Date of visit
- Adjuvant therapy
- Reversion of ileostomy
- Details on recurrence, including date and method of diagnosis, site of recurrence and treatment consequences
- Details on complications
- Date and cause of death

15.7 Amendments

Amendments are changes made to the research after a favourable opinion by the accredited METC has been given. All amendments will be notified to the METC that gave a favourable opinion.

A 'substantial amendment' is defined as an amendment to the terms of the METC application, or to the protocol or any other supporting documentation, that is likely to affect to a significant degree:

- the safety or physical or mental integrity of the subjects of the trial;
- the scientific value of the trial;
- the conduct or management of the trial; or
- the quality or safety of any intervention used in the trial.

All substantial amendments will be notified to the METC and to the competent authority.

Non-substantial amendments will not be notified to the accredited METC and the competent authority, but will be recorded and filed by the sponsor.

15.8 Annual progress report

The investigator will submit a summary of the progress of the trial to the accredited medical ethical committee once a year. Information will be provided on the date of inclusion of the first subject, numbers of subjects included and numbers of subjects that have completed the trial, serious adverse events/ serious adverse reactions, other problems, and amendments.

15.9 End of study report

In case the study is ended prematurely, the investigator will notify the accredited METC within 15 days, including the reasons for the premature termination. Within one year after the end of the study, the investigator/sponsor will submit a final study report with the results of the study, including any publications/abstracts of the study, to the accredited METC.

The sponsor will notify the accredited METC and the competent authority of the end of the study within a period of 90 days. The end of the study is defined as the last patient's last visit.

In case the study is ended prematurely, the sponsor will notify the accredited METC and the competent authority within 15 days, including the reasons for the premature termination. Within one year after the end of the study, the investigator/sponsor will submit a final study report with the results of the study, including any publications/abstracts of the study, to the accredited METC and the Competent Authority.

15.10 Monitoring, audit and inspection

Governors will be appointed to monitor trial progress on site, as frequently as seen necessary. The medical ethical review board of the coordinating centre (VU University Medical Centre) will register the trial at the clinical research bureau (CRB).

15.11 Authorship eligibility guidelines and any intended use of professional writers

All presentations and publications will be in the name of the 'COLOR III Study Group'. The sponsor will have no influence on implementation of the research and content of publications.

Nationally assessed data, on for example quality of life and costs can be published or presented by subgroups of authors without international consent. Publication or presentation of these data can only be possible when the authors state that the corresponding patients were included in the COLOR III trial. If a centre violates these rules, exclusion from the COLOR III trial and exclusion from authorship will be the consequence. Publication of data will not take place until accrual of patients has been completed.

15.12 Trial Management Committee

The Protocol and Writing Committee is responsible for the organisation of the trial. The Protocol Committee is responsible for the publication and presentation of all data. Publications will be coordinated by the Coordinating Centre.

16 SAFETY REPORTING

16.1 Section 10 WMO event

In accordance to section 10, subsection 4, of the WMO, the investigator will inform the subjects and the reviewing accredited medical ethical committee if anything occurs, on the basis of which it appears that the disadvantages of participation may be significantly greater than was foreseen in the research proposal. The study will be suspended pending further review by the accredited medical ethical committee, except insofar as suspension would jeopardise the subjects' health. The investigator will take care that all subjects are kept informed.

16.2 AEs and SAEs

16.2.1 Adverse events (AEs)

Adverse events are defined as any undesirable experience occurring to a subject during the study, whether or not considered related to TaTME. All adverse events reported spontaneously by the subject or observed by the investigator or his staff will be recorded.

16.2.2 Serious adverse events (SAEs)

A serious adverse event is any untoward medical occurrence or effect that:

- results in death;
- is life threatening (at the time of the event);
- requires hospitalisation or prolongation of existing inpatients' hospitalisation
- results in persistent or significant disability or incapacity;
- is a new event of the trial likely to affect the safety of the subjects, such as an unexpected outcome of an adverse reaction, disease, major safety finding from a newly completed animal study, etc.
- Any other important medical event that may not result in death, be life threatening, or require hospitalisation, may be considered a serious adverse experience when, based upon appropriate medical judgement, the event may jeopardise the subject or may require an intervention to prevent one of the outcomes listed above

Reporting procedure applies to all (S)AE's occurring from the time a subject gives consent until 30 days after surgery and to any SAE that occurs after the 30-day period, if it is considered to have a reasonable possibility to be related to the protocol treatment or study participation.

A life threatening SAE, or SAE with death as a result, must be reported within 7 days after the local investigator has been informed. Other SAEs must be reported within 15 days . The study coordinator is responsible for reporting SAEs at CCMO module 'ToetsingOnline'.

For individual sites, the local investigator completes the SAE form providing as much detailed information as known and relevant to the event. The local investigator sends the complete SAE form by e-mail to the study coordinator within 24 hours of discovery of the event. Thus, the coordinating investigator will be notified by email or telephone within 24 hours after discovery of the event. Using the CCMO module 'ToetsingOnline', all SAEs will be reported to the CCMO and central medical ethical committee. By means of this website notifications will be sent to the relevant authorities. The reporting will occur within 15 days after the investigator has first received information on the SAE. For fatal or life-threatening cases, a preliminary report will be offered within 7 days followed by a complete report within 8 days.

The following SAE's do not require immediate reporting but will be reported once yearly in line-listings to the accredited medical ethical review board that approved the protocol:

- Elective hospitalisation for pre-existing conditions that have not been exacerbated by trial treatment
- A hospitalisation which was planned before the subject consented for study participation and where admission did not take longer than anticipated
- Social and/or convenience admission to a hospital
- Disease recurrence in the follow-up year requiring hospitalisation

16.2.3 Follow-up of adverse events

All AEs will be followed until they have abated, or until a stable situation has been reached. Depending on the event, follow up may require additional tests or medical procedures as indicated, and/or referral to the general physician or a medical specialist. SAEs need to be reported till end of study within the Netherlands, as defined in the protocol.

16.3 Data Safety Monitoring Board (DSMB)

This study is considered a medium risk trial. To assure proper data safety monitoring and relevance a DSMB will be installed. The DSMB will guard the safety of the included patients, give advice on continuation of the study upon superiority of one of the types of treatment, and will guard the methodological quality of the study. Furthermore, to keep insight in SAE's, the trial coordinator will communicate all SAE's to the independent monitor and to the Trial Steering Committee ([name], [name], [name], [name], [name], [name], [name], [name], [name], [name], [name], [name]) of this study. The Trial Steering Committee will comment on the reports.

The advice(s) of the DSMB will only be sent to the sponsor of the study. Should the sponsor decide not to fully implement the advice of the DSMB, the sponsor will send the advice to the reviewing METC, including a note to substantiate why (part of) the advice of the DSMB will not be followed.

Charter DSMB COLOR III trial

CONTENT	
1. Introduction	
Name of trial ISRCTN and/or EUDRACT number	COLOR III trial
Study risk classification	Medium
Objectives of trial, including interventions being investigated	The COLOR III trial is an international multicentre randomised study comparing short- and long term outcomes of TaTME and laparoscopic TME for rectal cancer. The study will include a quality assessment phase before randomisation to ensure required competency level and uniformity of the new TaTME technique and the laparoscopic TME. During the trial the clinical data will be reviewed centrally to ensure uniform quality. The primary endpoint of the COLOR III trial is quality of resection defined by involvement of CRM. Secondary endpoints include morbidity and mortality, residual mesorectum on postoperative MRI, local recurrence rate, disease-free and overall survival, percentage of sphincter saving procedures, functional outcome and quality of life.
Outline of scope of charter	The purpose of this document is to describe the roles and responsibilities of the independent DSMB for the COLOR III trial, including the timing of meetings, methods of providing information to and from the DSMB, frequency and format of meetings, statistical issues and relationships with other committees.
2. Roles and responsibilities	
A broad statement of the aims of the committee	To safeguard the interests of trial participants and assess the safety of the TaTME procedure during the trial.
Terms of reference	The DSMB should receive and review the safety data of this trial. The DSMB should inform the Chair of the Trial Steering Committee if, in their view: The number of (serious) adverse events is skewed between the groups. Interim review when 50% of the total 1104 patients are included. The DSMB will be supplied with all data to evaluate the number of (serious) adverse events in all groups at the above mentioned time points, the inclusion rate unexpected differences in endpoints between study arms and potential conflicts with new insights and/or developments within the field of rectal cancer.
Specific roles of DSMB	It is at the discretion of the DSMB to meet early in the course of the trial and to discuss the protocol with the interim analysis plan, and to have the opportunity to clarify any aspects with the principal investigators.
3. Composition	
Membership and size of the DSMB	DSMB members register their assent by confirming (1) that they agree to be on the DSMB and (2) that they agree with the contents of this Charter. The members are independent of the trial and have no competing interest that could impact on the trial. Also see the competing interest form (Annex

CONTENT

1).

The members of the DSMB for this trial are:

- (1) Prof. dr. [name] (Chair; Gastroenterologist, VUmc)
- (2) Prof. dr. [name] (Gastrointestinal Surgeon, AvL Amsterdam)
- (3) Dr. [name] (Statistician, VUmc)

The Chair is expected to facilitate and summarise discussions.

The trial office team will provide input to the production of the DSMB report.

The trial PI may be asked, and will be available, to attend open sessions of the DSMB meeting. The other trial group members will not usually be expected to attend but can attend open sessions when necessary.

4. Relationships

Clarification of DSMB role

No payments or rewards will be awarded to the DSMB.

Competing interests

Competing interests of DSMB members – financial matters, involvement in other trials or intellectual investment – should be disclosed (Annex 1).

DSMB members should not use interim results to inform trading in pharmaceutical shares, and careful consideration should be given to trading in stock of companies with competing products.

5. Organisation of DSMB meetings

Expected frequency of DSMB meetings

The DSMB will meet at least once in the first year after the start of patient inclusion. The DSMB will perform an interim analysis at two time points as mentioned before.

The meetings of the DSMB can be by conference call, as long as full discussion with all members can be guaranteed.

All sessions are in principle open, although the DSMB can decide otherwise.

6. Trial documentation and procedures to ensure confidentiality and proper communication

Intended content of material to be available in open sessions

Accumulated information relating to the trial's safety data will be presented. Other outcome measures (e.g. efficacy) may be presented, at the discretion of the DSMB.

The DSMB members will not be blinded to the treatment allocation.

Who will see the accumulating data and interim analysis

The DSMB will discuss the results of the interim analysis with the Trial Steering Committee. DSMB members do not have the right to share confidential information with anyone outside the DSMB, other than the Trial Steering Committee.

External evidence

The PI and trial coordinator will identify and circulate external evidence that can influence the trial.

To whom the DSMB will communicate the decisions/ recommendations that are reached

The DSMB reports its recommendations in writing to the Trial Steering Committee. This will be copied to the trial coordinator in time for consideration at a TSC meeting.

CONTENT

The DSMB members should store the papers safely after each meeting so they may check the next report against them. After the trial is reported, the DSMB members should destroy all interim reports.

7. Decision making

Decisions/recommendations open to the DSMB

Possible recommendations:

- No action needed, trial continues as planned
- Early stopping due, for example, to clear benefit or harm of TaTME, futility, or external evidence

Decisions or recommendations within the DSMB

Every effort should be made for the DSMB to reach an unanimous decision. If the DSMB cannot achieve this, a vote may be taken, although details of the vote should not be routinely included in the report to the TSC as these may inappropriately convey information about the state of the trial data.

It is important that the implications (e.g. ethical, statistical, practical, and financial) for the trial be considered before any recommendation is made.

Effort should be made for all members to attend. The trial coordinator will try to ensure that a date is chosen to enable this. Members who cannot attend in person should be encouraged to attend by teleconference. If, at short notice, any DSMB members cannot attend at all then the DSMB may still meet if at least one statistician and one clinician, including the Chair (unless otherwise agreed), will be present. If the DSMB is considering recommending major action after such a meeting the DSMB Chair should talk with the absent members as soon after the meeting as possible to check they agree. If they do not, a further teleconference should be arranged with the full DSMB.

If the report is circulated before the meeting, DSMB members who will not be able to attend the meeting may pass comments to the DSMB Chair for consideration during the discussions.

If a member does not attend a meeting, it should be ensured that the member is available for the next meeting. If a member does not attend a second meeting, they should be asked if they wish to remain part of the DSMB. If a member does not attend a third meeting, they should be replaced.

8. Reporting

Recommendations/decisions of the DSMB

The DSMB will report their recommendations/decisions in a letter to the Trial Steering Committee, within 4 weeks after the meeting. A copy of this letter will be lodged with the trial coordinator.

Disagreement between the DSMB and TSC

If the DSMB has serious problems or concerns with the Trial Steering Committee decision a meeting of these groups should be held. The information to be shown would depend upon the action proposed and the DSMB's concerns. Depending on the reason for the disagreement confidential data will have to be revealed to all those attending such a meeting. The meeting will be chaired by a senior member of the trials office staff or an external expert who is not directly involved with the trial.

9. After the trial

Publication of results

If requested by the DSMB, a meeting at the end of the trial will be held to allow the DSMB to discuss the final data with the principal trial investigators

CONTENT

and give advice about data interpretation

The DSMB will be given the opportunity to read and comment on any publications before submission, especially with respect to reporting of any DSMB recommendation regarding termination of a trial

The DSMB may discuss issues from their involvement in the trial when permission is agreed with the overseeing committee.

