Interim analysis	Planned at 50% of the inclusion with regards to the sample size and conversions

TRIAL SUMMARY

Introduction and background

The quality of rectal cancer surgery has improved during the last decades with the total mesorectal excision (TME) technique, adaptation of laparoscopic surgery and extralevatory approach for abdominoperineal resection (APR). Nevertheless, surgery for mid and low rectal cancer is associated with relative high rates of conversions, permanent colostomies, and incomplete mesorectal excisions and relative high rates of circumferential resection margin (CRM) involvement resulting in significant number of local recurrences.

The transanal TME (TaTME) has been developed with use of laparoscopic single port platforms to improve the quality of the TME procedure in mid and low rectal cancer. In TaTME, the tumour is distally approached through the anus with laparoscopic instruments. In TaTME, the tumour is distally approached through the anus with laparoscopic instruments. Latest systematic review of cohort studies showed that the TaTME technique is feasible and facilitates difficult resections in the lower pelvis. A low conversion rate and more sphincter saving procedures are reported. Moreover the current data from cohort studies have shown that the TaTME procedure is safe and is associated with less conversions and less morbidity in experienced centres compared with laparoscopic TME.

. Before adaptation of the TaTME as standard surgical therapy for mid an low rectal cancer, a well-designed study is essential to demonstrate its efficacy and safety in a multicentre randomised setting. The primary concern is oncological safety in terms of local recurrence rate. Secondary concerns are conversion rate, permanent colostomy rate and safety in terms of pathology, morbidity and functional outcome.

Study design

The COLOR III trial is an international multicentre randomised study comparing short- and long term outcomes of TaTME and laparoscopic TME for rectal cancer. The design is non-inferiority compared to conventional laparoscopic surgery. The study will include a quality assessment phase before randomisation to ensure required competency level and uniformity of the new TaTME technique and the laparoscopic TME. During the trial the clinical data will be reviewed centrally to ensure uniform quality.

Endpoints

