3.2 Primary endpoint/outcome

The primary endpoint is the percentage of patients with local recurrence after 3 years of follow-up.

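### At the one interim look that is named, no patient will have 3-year data, yet the DSMB charter lists benefit and futility stops, states a different primary endpoint and opens interim results to the Trial Steering Committee

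*Protocol*

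**What the plan says.** **Endpoint.** Protocol section 3.2: "The primary endpoint is the percentage of patients with local recurrence after 3 years of follow-up". Section 14.1 sizes the trial on the same endpoint. The charter's introduction (section 16.3, item 1) instead gives involvement of the CRM as primary and lists local recurrence among the secondary endpoints.

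**Timing and purpose of the interim.** The synopsis says: "Planned at 50% of the inclusion with regards to the sample size and conversions". Charter item 2 places the review at 50% of 1104 patients included. Charter item 5 says: "The DSMB will perform an interim analysis at two time points as mentioned before". No second time point is named, although item 5 also asks for at least one meeting in the first year.

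**What the board may advise.** Charter item 7 offers continuation as planned or "Early stopping due, for example, to clear benefit or harm of TaTME, futility, or external evidence". The body of section 16.3 adds that the board will "give advice on continuation of the study upon superiority of one of the types of treatment".

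**Who sees what.** Charter item 5: "All sessions are in principle open, although the DSMB can decide otherwise". Under item 6 the board is unblinded, open sessions present safety data, and efficacy may be presented there if the board so decides. Item 6 also states: "The DSMB will discuss the results of the interim analysis with the Trial Steering Committee".

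**Who receives the advice.** The body of section 16.3 says: "The advice(s) of the DSMB will only be sent to the sponsor of the study". Charter items 6 and 8 send it in writing to the Trial Steering Committee, with a copy to the trial coordinator.

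**The concern.** There are two separate problems.

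The first is what the look can support. The charter allows stopping for benefit or futility, and section 16.3 speaks of superiority, at a time when the endpoint that defines the trial is almost unobserved. A board that works from the charter could also take CRM involvement as the decisive outcome, because the charter tells it so.

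The second is who learns the comparative results. Allocation is not blinded (section 4). Conversion is the surgeon's decision (section 9.3), and examinations beyond the schedule are left partly to the attending surgeon's preference (section 12.1). If those who run the trial know how the arms compare while inclusion continues, this can affect which patients are entered, when an operation is converted and how intensively recurrence is sought. Such operational bias cannot be removed at the analysis stage, and a non-inferiority conclusion is sensitive to it.

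**Working it through.** **1. The plan's own figure.** Inputs from section 14.1 and the synopsis: 5% local recurrence at 3 years (taken as equal in both arms), margin 4 percentage points, one-sided 2.5%, power 80%, allocation 2:1, 5% drop-out.

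Control arm: n = (1.960 + 0.842)² × 0.05 × 0.95 × (1 + 1/2) / 0.04² = 7.849 × 0.0475 × 1.5 / 0.0016 ≈ 349.5. Total = 3 × 349.5 ≈ 1,048.6, and 1,048.6 / 0.95 ≈ 1,104. The stated size is reproduced, with the whole one-sided 2.5% used at the final test.

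**2. When the 50% look falls.** Half of 1104 is 552. The synopsis gives the inclusion period both as four years and as three. With even accrual, 552 is reached at 2.0 or 1.5 years. With linearly ramping accrual, it is reached at 4 × √0.5 = 2.83 or 3 × √0.5 = 2.12 years. All four values are below 3 years, so no patient has 3-year follow-up. Under even accrual, inclusion would have to last more than 6 years before any patient had 3-year data at the halfway point.

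**3. Recurrences expected by then.** Assumptions: constant hazard giving 5% at 3 years in both arms, surgery at randomisation, even accrual.

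- Hazard h = −ln(0.95)/3 = 0.0171 per year.
- Expected events = 552 × [1 − (1 − e^(−ht))/(ht)].
- t = 1.5 (three-year inclusion): 7.0.
- t = 2.0 (four-year inclusion): 9.3.
- Full trial at 3 years: 1104 × 0.05 = 55.2.
- Share observed: 7.0/55.2 = 13%; 9.3/55.2 = 17%.

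Linear ramping gives 6.6 and 8.8, so the result does not depend on the accrual shape. About a third of these events, 2 to 3, would be in the control arm.

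**4. What 7 to 9 events can show.** At 2:1, the standard error of the log hazard ratio is about 1/√(events × 2/9). That is 0.80 with 7 events and 0.71 with 9. The 95% interval then extends by a factor of exp(1.96 × 0.80) ≈ 4.8 or exp(1.96 × 0.71) ≈ 4.0 in each direction. The margin of 9% against 5% is a hazard ratio of ln(0.91)/ln(0.95) ≈ 1.84. The interval is far too wide to separate equality from the margin in either direction.

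**5. Passages that do not agree.**

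| Topic | One place | Another place |
|---|---|---|
| Primary endpoint | Section 3.2, section 14.1, synopsis: local recurrence at 3 years | Charter item 1: CRM involvement |
| Interim looks | Synopsis, charter item 2: one, at 50% inclusion | Charter item 5: two |
| Recipient of advice | Section 16.3 body: the sponsor alone | Charter items 6 and 8: Trial Steering Committee, copy to trial coordinator |
| Protection of interim data | Charter item 7: details of votes not routinely reported to the committee, since they could reveal the state of the data | Charter item 6: the interim results themselves are discussed with that committee |

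**The case against.** The best reply is that the charter is mainly a safety document. Its stated aim is to protect participants, and the stopping reasons are given as examples. Two of them, harm and external evidence, can be judged at 552 patients from adverse events, conversions and outside data. This stands: the timing objection covers only benefit and futility on local recurrence. If the board works from the charter's own endpoint, CRM results would be available at that time. That may explain the wording, but it leaves the contradiction with section 3.2 in place.

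The openness should not be exaggerated either. The board may close a session, the principal investigator attends if asked, and other trial group members are not normally expected. These are discretionary limits, and none applies to the discussion of results with the Trial Steering Committee.

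Three stronger readings are tempting but not supported:

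- **The interim may change the sample size.** A reader might infer this from the synopsis. No re-estimation rule is stated, and the charter's listed recommendations are to continue or to stop early. The board also receives the inclusion rate, so the phrase may refer to recruitment progress. It needs clarifying, and no range of revised sizes can be derived from it.
- **Type I error is inflated.** This would require an unadjusted interim test of non-inferiority, and none is described. The documents speak of superiority and clear benefit, and a futility stop cannot raise type I error. Any boundaries may be in the SAP, which is not shown, or in the interim analysis plan that charter item 2 mentions. Their absence here is not a fault. A boundary would not, however, supply the missing follow-up or change who sees the results.
- **There is only one interim.** The documents support only that one time point is named while two are mentioned. If the first-year meeting is the second, it would hold even less primary-endpoint information.

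**Conclusion.** The point holds in this form. On the planned calendar, the one named look comes before any patient has 3-year data and with about 7 to 9 of about 55 expected recurrences (13-17%). A stop for benefit or futility, or advice on superiority, could not then rest on the endpoint of section 3.2. The charter states another primary endpoint, disagrees with itself on the number of looks, and disagrees with the body of section 16.3 on who receives the advice. Discussing unblinded interim results with the Trial Steering Committee during inclusion is an avoidable source of operational bias, and the charter recognises that hazard where it restricts vote details.

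The timing result rests on the stated three- or four-year inclusion. The event counts also assume a constant hazard, 5% at 3 years in both arms and surgery at randomisation; any delay to surgery would lower them. The size of the operational bias cannot be calculated from the documents. The contradictions and the access to results are read directly from the text and need no assumption.

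**What to change.** Amend the charter, section 16.3 and the synopsis:

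1. Present comparative interim data only in closed DSMB sessions. The Trial Steering Committee receives the recommendation and not the results.
2. Reconcile the two reporting lines so that section 16.3 and the charter name the same recipients.
3. Correct the charter's primary endpoint to local recurrence at 3 years, as in section 3.2.
4. State the number and timing of interim looks in the same way throughout. State that the look at 552 patients reviews safety and conversions and does not test the primary endpoint, so that the full one-sided 2.5% stays with the final analysis.
5. Say what the synopsis means by linking the interim to the sample size. If a size check is intended, base it on blinded pooled data.

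The cost is a revision of wording, with no change to the sample size, visits or data collection. The sponsor gives up an early efficacy option on the primary endpoint, which the timing could not have supported. Safety review by the board is unaffected.
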